4.3.2 Control group

The control group receives standard health education without systematic RT. Activities include monthly 60-minute bone-health lectures (OP pathophysiology, nutritional guidance, fall-prevention strategies), delivered by hospital orthopaedic and community clinic staff, with

printed educational materials. Group discussion sessions are held every 4 months. Weekly telephone or WeChat follow-up by research staff provides general health advice (e.g., daily 20–30 minute walks), maintaining comparable contact frequency without introducing RT. This “attention control” design ensures that contact and engagement levels are balanced between groups.

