Decline in muscular strength is a primary contributor to falls, fractures, and functional disability. RT can significantly improve muscle strength, balance, and physical function in older adults, thereby reducing fall risk. Cao et al. (2021), writing in *Ageing Research Reviews*, reported that participants in a progressive RT programme (twice weekly, three sets of 8–12 repetitions at 60–80% 1RM for 12 weeks) demonstrated lower-extremity strength gains of 38.5–45.2%, grip strength improvements of 18.7–22.3%, and a 0.17–0.20 m/s increase in 6-metre gait speed [23].

Strength gains are closely linked to improved motor-unit recruitment efficiency, increased muscle-fibre cross-sectional area, and optimised neural control. Quadriceps strength, in particular, exhibits a significant inverse association with fall risk and is therefore a key target for exercise intervention. Rabinovich et al. reported that following high-intensity RT combined with impact training, quadriceps strength increased by over 35% while five-times sit-to-stand test time decreased by more than 20%, demonstrating clinically meaningful functional improvement [24].

Improvements in physical function are further reflected in SPPB and TUG outcomes. A 2022 meta-analysis of 34 RCTs showed that, compared with health education or usual activity, RT significantly improved gait speed (MD = 0.23, 95% CI: 0.07–0.39), appendicular skeletal muscle mass index (MD = 0.24, 95% CI: 0.08–0.40), and grip strength (MD = 2.75, 95% CI:

1.35–4.15) among older adults with muscle wasting [25]. A 2022 meta-analysis of 14 RCTs demonstrated that ≥ 12 weeks of progressive machine-based RT improved TUG (SMD = -0.62), gait speed (SMD = 0.46), sit-to-stand performance (SMD = -0.92), SPPB (SMD = 0.63), and six-minute walk test (SMD = 0.56) relative to usual activity [26].

RT reduces fall risk through three mechanisms: strengthening of lower-extremity musculature to enhance support, improving proprioception for superior postural control, and accelerating neuromuscular reaction time to shorten the fall-response interval. A 2021 meta-analysis of 14 RCTs showed that lower-extremity RT improved TUG (MD = -1.17 , 95% CI: -1.91 to -0.43), single-leg stance time with eyes open (MD = 3.92 , 95% CI: 2.46 – 5.38), and functional reach distance (MD = 4.85 , 95% CI: 3.07 – 6.63), compared with usual activity [27].

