1.4 Research Objectives and Innovations

1.4.1 Overall research objective

The overarching objective is to validate the comprehensive benefits of “community-based

smart RT” for BMD, muscular function, and quality of life (QoL) among older adults with OP, and to establish a sustainable implementation pathway. Specifically: (a) quantify the effect of 8-month RT on lumbar spine BMD through an RCT, with an expected increase of $\geq 3\%$ (benchmarked against the IOF clinical significance threshold); (b) design a long-term intervention strategy with 8 months of supervised training (twice weekly) followed by 12 months of low-frequency maintenance (once monthly); and (c) develop an integrated smart elderly care system featuring real-time wearable monitoring, AI-driven exercise prescription adjustment, and community-station offline supervision, achieving “data–professional–family” three-tier coordination.

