		Precautions	
1. Do not hold your breath during training to prevent cardiovascular disease
 
2. When exercising, pay attention to inhaling when exerting force and exhaling when relaxing
 
3. After exercise, use the smart health bracelet to remind the elderly to fill in the exercise diary.

		
4. Before exercise, self-assess whether there are any discomfort symptoms, blood pressure and blood sugar control, and stop exercising if you feel uncomfortable
 
5. If the patient experiences dizziness, chest tightness, difficulty breathing and other discomfort symptoms during exercise, stop exercising immediately and contact the researcher immediately
 
6. Gradually increase the intensity of exercise to ensure patient tolerance.

Health Education Program	Expert Lectures	
1. Definition, classification and harm of the disease, etc., to make patients aware of the susceptibility of the disease
 
2. The effect of exercise on osteoporosis and the harm of inactivity, etc., to make patients aware of the benefits of exercise and the severity of inactivity
 
3. Analyze the patient's current movement disorders, gradually eliminate the obstacles they may encounter, and correct incorrect cognition

	1 offline group class per month	
1. Patients share their current feelings about exercise and the obstacles they encounter
 
2. Patients with strong exercise execution ability share their experiences
 
3. Review the effects of exercise
 
4. Provide supplementary health education

	Once a week, offline action guidance, error correction and adjustment	
1. Ask patients about their individual differences in the implementation of the plan
 
2. Encourage patients to keep exercising
 
3. Understand and guide patients on how to master exercise methods, and timely micro-control the amount of exercise
 
4. Export the patient's health data and exercise status analysis for this week through the smart bracelet data platform and use the data to make patients more confident to continue to persist.
 
5. Ask patients about their exercise status in the past week and encourage them to express their feelings about exercise.
 
6. Emphasize precautions during exercise to ensure patient safety

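### The control arm's education lists nutrition, fall prevention and walking advice that the training arm's does not, so the contrast is not shown to be resistance training plus education versus the same education

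*Protocol*

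**What the plan says.** **Aim and comparator.** Section 1.4.1 sets out to "quantify the effect of 8-month RT on lumbar spine BMD through an RCT". Section 3.3.1 names the comparator as a health education control group, and H6 in section 3.2.6 calls it usual health education.

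**Control arm (4.3.2).** It receives "monthly 60-minute bone-health lectures (OP pathophysiology, nutritional guidance, fall-prevention strategies"), printed materials, and a group discussion every four months. In addition: "Weekly telephone or WeChat follow-up by research staff provides general health advice (e.g., daily 20–30 minute walks"). The section concludes that the attention-control "design ensures that contact and engagement levels are balanced between groups".

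**Training arm (4.3.1).** The expert lectures in Table 4.3.1 (1) cover what the disease is and the harm it does, then "The effect of exercise on osteoporosis and the harm of inactivity, etc", then the patient's own obstacles to movement. The monthly group class covers sharing of experience, a review of what exercise does, and an open item, "Provide supplementary health education". A weekly session deals with technique, encouragement and wristband data. The text of 4.3.1 adds monthly group lectures without stating their content, weekly WeChat contact about questions and adherence, and weekly one-on-one correction of technique.

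**The concern.** To attribute a between-arm difference to resistance training, both arms need the same background, with training the only addition. Followed as written, the two education programmes differ in content, and the items listed only for controls bear on the trial's own outcomes. Fall-prevention teaching bears on the fall incidence rate ratio (4.4.2). Walking advice bears on SPPB, which contains 4-metre gait speed (4.4.1). Nutrition bears on BMD, and section 3.3.3 itself names calcium and vitamin D intake as covariates.

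At stake is interpretation. A small or null difference in falls could mean that training does little, or that only the controls were taught fall prevention. The protocol as it stands cannot separate the two. Section 2.2.2 criticises earlier trials for poorly standardised control conditions, so the point falls within a standard that the protocol sets for itself.

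**Working it through.** The protocol states no sample size, power or effect for the control components, so there is no figure to reproduce. The check is a comparison of content, followed by two counts that bear on direction.

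**1. Content side by side**

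| Element | Control (4.3.2) | Training (4.3.1, table and text) |
|---|---|---|
| Disease knowledge | Listed | Listed |
| Nutrition | Listed | Not listed |
| Fall prevention | Listed | Not listed |
| Walking advice | Listed as an example of weekly general advice | Not listed |
| Printed educational materials | Listed | Not listed |
| Benefits of exercise, obstacles to it | Not listed | Listed |
| Open or unspecified education | – | Supplementary education item; monthly lectures without stated content |
| Wristband, reminders, technique sessions | Not listed | Listed |

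The last row belongs to the intervention and is expected to differ. The rows for nutrition, fall prevention, walking and printed materials are general education. They differ with no stated reason, and no sentence bridges them.

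**2. What the balance claim covers.** Section 4.3.2 claims balance of contact and engagement only. It does not claim that content is shared.

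**3. Activity time named in the text**
- Walking example: 7 × 20 to 7 × 30 = 140–210 minutes a week.
- Resistance training, text of 4.3.1: 3 × 30 to 3 × 50 = 90–150 minutes a week.
- Resistance training, Table 4.3.1 (1): 3 × 40 to 3 × 60 = 120–180 minutes a week.

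The advised walking is not trivial in time. But it is advised rather than delivered, and minutes are not dose: section 1.3.1 ties BMD gain to intensity.

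**4. Differences that may act the other way.** Eight months is 8 × 52/12 ≈ 35 weeks. Training sessions are not counted.
- Control contacts: 8 lectures + 2 discussions + 35 weekly contacts = 45.
- Training arm, low count: 8 monthly + 35 WeChat + 35 technique sessions = 78, and 78/45 ≈ 1.7.
- Training arm, high count (group class, lecture and on-site supervision counted separately): 8 + 8 + 8 + 35 + 35 = 94, and 94/45 ≈ 2.1.

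More contact, with a wristband and reminders, could widen differences on effort-dependent or self-reported outcomes.

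**5. Whether the data could separate the effects later.** Baseline physical activity is a covariate (3.3.3). The only activity row in the schedule of 3.3.4 is ticked at T3, and calcium and vitamin D intake has no row. The text below that table says T2 repeats the full baseline battery, which might include activity, but the table does not show it. Measurement at the primary time point of walking taken up by controls is therefore not assured.

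**The case against.** **The listed gap may not be a delivered gap.** The training arm's lecture items are open-ended, its group class has an unspecified education item, its monthly lectures have no stated content, and section 4.3.3 refers to an operations manual that is not shown. This stands. A reader might infer that the training arm gets no teaching on nutrition or falls, and the document does not establish that. The remaining defect is that the protocol does not fix the matter, so staff who follow it could deliver either version.

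**Walking is only an example.** A reader might infer that controls are coached every week towards a daily walking target. The text does not support this: walking illustrates general advice, with no target, log, progression or adherence check.

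**The direction is not established.** A reader might conclude that all effects are pulled towards zero, with a calculable loss of power. No passage gives an effect for walking advice or lectures, no sample size is stated, and the contact counts above show influences that may run the other way. Any power figure would rest on an invented attenuation fraction and an assumed number per arm, so none is offered.

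**The comparator is not mislabelled.** Lectures and general advice are health education, and some of the evidence in section 1.3.2 has that comparator: "compared with health education or usual activity, RT significantly improved gait speed". An attention control that may be conservative is a legitimate choice. This also stands. The issue is whether the general education is common to both arms, not whether education is an acceptable control.

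**Conclusion.** The point holds as one of unreconciled content. Read as written, the arms differ by more than resistance training and its support, because section 4.3.2 lists nutrition, fall prevention, general advice with walking as an example, and printed materials that 4.3.1 does not list. The contrast is not shown to be training plus education against the same education.

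Control-only content on falls and activity could plausibly attenuate the fall rate ratio and the SPPB difference. For lumbar spine BMD this is less certain. The size cannot be given, and the net direction is unknown because the extra technique sessions, wristband and reminders may offset or outweigh it. Opposing influences of unknown size do not make the contrast interpretable.

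The conclusion assumes only that the listed content describes what will be delivered. If the open items in 4.3.1 are meant to carry the control curriculum, saying so resolves the point.

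**What to change.** Reconcile 4.3.1 (Table 4.3.1 (1) and the personnel-support text) with 4.3.2:

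- Define one common background programme for both arms: the same bone-health lecture curriculum, the same printed materials and the same script of general advice for the weekly contact.
- State that resistance training and its smart support are the only added element in the training arm.
- Name the comparison in 1.4.1, 3.2.6 and 3.3.1 as smart resistance training plus common education versus common education.

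Which clinical advice the common programme contains is for the investigators to decide. The statistical requirement is only that it be shared.

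Cost: protocol wording, one curriculum and one script. Both arms already have monthly lectures and weekly remote contact, so no new visits are needed. The small downside is slightly longer education contact in the training arm. Section 4.7.1 gives ethical approval as pending, so the change is cheap now.

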3.3.4 Detailed measurement schedule

表 3.3.4 Data measurement schedule 数据测量时间表						
Measurement field 测量领域	Specific measurement items 具体测量项目	T0	T1	T2	T3	备注
		Before intervention 干预前	4 months 4 个月	8 months 8 个月	14 months 14 个月	
Demography 人口学	Age, gender, education level, medical history, medication use	✓				Baseline collection only
Physical indicators	Height, weight, BMI	✓		✓	✓	Tracking changes

身体指标						
BMD 骨密度 DXA	Lumbar spine and hip BMD	✓	✓	✓	✓	4 months DXA As needed
Body functions 身体功能	SPPB Overall Rating	✓	✓	✓	✓	
	Overall balance	✓	✓	✓	✓	
	4-meter pace	✓	✓	✓	✓	
	5 Sit-to-Stand (5STS)	✓	✓	✓	✓	
	Grip strength (HGS)	✓	✓	✓	✓	Intermediary Indicators
Questionnaire 问卷调查	SF-36	✓	✓	✓	✓	
	FES-1	✓	✓	✓	✓	
	eHLQ、TAM	✓	✓	✓		Track
Implementation process 实施过程	Training compliance and dosage (platform log and manual log)		✓	✓		Continuous recording to stage nodes
Safety Monitoring 安全监测	Cumulative number of falls & adverse events			✓	✓	Summary
	New fracture				✓	
Behavior Tracking 行为追踪	Daily physical activity after intervention				✓	

Measurements are conducted at four time points: T0 (baseline, 1 week pre-randomisation) includes comprehensive demographic, clinical, functional, and questionnaire assessments; T1 (mid-intervention, 4 months) comprises streamlined assessments covering DXA (resources permitting), functional tests, adherence data, and questionnaires; T2 (end of intervention, 8 months) repeats the full baseline assessment battery plus cumulative adverse events; and T3 (follow-up, 20 months) evaluates long-term outcomes including new fractures, BMD maintenance, and post-intervention physical activity.

Chapter 4 Overall Methodology and Ethics

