Periodised progression follows dual-indicator control: volume progression (one additional set per exercise every 4 weeks, maximum 3 sets), intensity progression (resistance-band upgrade when RPE ≤ 4 with 15 standard repetitions), and density progression (inter-set rest reduced from 120 seconds to 75 seconds after week 12).

Smart components: each participant receives a Huawei Band 10 smart wristband that monitors heart rate, fall events, and blood pressure via Bluetooth synchronisation to the community health management platform. Training completion is recorded through WeChat-based manual check-in. A WeChat mini-programme delivers daily training prescriptions with illustrated guidance. The system includes automated training reminders and safety alerts (abnormal heart-rate detection triggers rest prompts and staff notification).

Personnel support: trained staff provide in-person guidance during the first week, with monthly on-site supervision thereafter. A designated team member contacts each participant weekly via WeChat to address questions and maintain adherence. Health education includes monthly group lectures and weekly one-on-one technique correction sessions.

Safety measures: pre-training medical screening (physical examination and exercise-risk assessment), individualised modifications for comorbidities (e.g., extended warm-up and blood-pressure monitoring for hypertensive patients), on-site emergency equipment (first-aid kit, AED), and a formal adverse-event reporting mechanism with monthly review and immediate reporting of serious events to the ethics committee.

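### Section 4.3.2 says staff contact is balanced between arms, but the protocol's own schedules give the intervention arm about three to six times as many in-person contacts

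*Protocol*

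**What the plan says.** Section 4.3.2 describes the comparator as an attention control and states as a fact that the "design ensures that contact and engagement levels are balanced between groups". Its contents are a monthly 60-minute lecture, weekly telephone or WeChat follow-up, and discussion groups: "Group discussion sessions are held every 4 months".

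Section 4.3.1 describes the intervention arm's contacts in two places.

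- The text under personnel support: "trained staff provide in-person guidance during the first week, with monthly on-site supervision thereafter". It adds: "A designated team member contacts each participant weekly via WeChat to address questions and maintain adherence". On education it says: "Health education includes monthly group lectures and weekly one-on-one technique correction sessions".
- Table 4.3.1 (1), in the health education rows, lists "1 offline group class per month" and "Once a week, offline action guidance, error correction and adjustment".

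Section 4.1.1 describes outcome assessors as blinded and says nothing of participants. Section 4.4.1 makes SF-36 PCS and MCS primary outcomes at T2, beside lumbar spine BMD and SPPB. FES-I and pain VAS are secondary (Section 4.4.2).

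**The concern.** The purpose of an attention control is to remove staff attention as an explanation for a difference between arms. The protocol says that this has been achieved, but its own schedules match only the remote contact and the lecture.

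The extra contact is also more than exercise delivery. According to Table 4.3.1 (1), staff use the weekly session to encourage participants, invite them to talk about how they feel about exercising, and show them their bracelet data to build confidence. The control arm has no face-to-face counterpart.

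The outcomes at stake are the self-reported ones: SF-36 PCS and MCS, FES-I and pain. Participants know whether they train, and it is plausible that such answers respond to personal attention. The balance sentence is the protocol's only stated safeguard against that explanation. A report that repeated it would rest on a property the design does not have. Section 2.2.2 itself criticises earlier trials for poorly standardised control conditions that may have inflated effects.

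**Working it through.** The protocol gives no number of contacts, so there is no figure to reproduce. The check counts planned contacts from the stated frequencies.

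**Inputs**

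- Length: 8 months, from Section 3.3.4 ("T2 (end of intervention, 8 months) repeats the full baseline assessment battery"). 8 × 52/12 = 34.7, taken as 35 weeks.
- Control, in person (Section 4.3.2): 8 monthly lectures + 8/4 = 2 discussions = 10.
- Intervention, in person (Section 4.3.1): 35 weekly one-on-one sessions; 8 monthly lectures; about 7 supervision visits after the start; 1 to 3 first-week sessions (assumed, as the number is not given); and 8 group classes if these are separate from the lectures.
- Remote: 35 weekly contacts in each arm.

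**Counts under each reading**

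The control arm has 10 in-person contacts, and 10 + 35 = 45 contacts in all.

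| Reading of the intervention schedule | In person | Ratio to 10 | All contacts | Ratio to 45 |
|---|---|---|---|---|
| All other visits fall within the weekly session | 35 | 3.5 | 70 | 1.6 |
| Weekly session + lecture | 35 + 8 = 43 | 4.3 | 78 | 1.7 |
| As above + supervision + 1 first-week session | 43 + 7 + 1 = 51 | 5.1 | 86 | 1.9 |
| Same, with 3 first-week sessions | 43 + 7 + 3 = 53 | 5.3 | 88 | 2.0 |
| Same, with class separate from lecture | 53 + 8 = 61 | 6.1 | 96 | 2.1 |

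**Sensitivity**

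- With a month taken as 4 weeks (32 weeks), the first row falls to 32/10 = 3.2 and the third to (32 + 8 + 7 + 1)/10 = 4.8.
- If the weekly session were remote, against the table's word for it (offline), in-person contacts would be 8 + 7 + 3 = 18 against 10, a ratio of 1.8. If it were also the same event as the weekly WeChat contact, all contacts would be 18 + 35 = 53 against 45, a ratio of 1.2. That is the least unequal reading, and the in-person imbalance remains.
- Training sessions are not counted, because Section 4.3.1 does not say that staff attend each one. If all three a week were attended, the count would be 3 × 35 + 8 = 113 against 10, a ratio of 11.3.

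These are contacts, not minutes. A duration is given for the control lecture, but none for the intervention arm's staff contacts, so time cannot be compared.

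**The case against.** The strongest reply has four parts.

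1. **The count depends on the reading.** In-person guidance in week 1 followed by monthly on-site supervision sits uneasily with a weekly offline session. Section 1.4.5 gives another picture again, with weekly telephone follow-up and periodic home visits. The monthly class may be the same event as the monthly lecture. This stands. A reader might take a factor of five as established, but it is only the central reading of a range of about 3 to 6.
2. **The trial compares programmes.** Section 3.3.1 sets smart RT against health education, and Section 1.4.1 states the objective in terms of community-based smart RT. Randomisation supports that contrast for every outcome, SF-36 included. This stands too. A reader might infer that the SF-36 comparison is invalid, or that the protocol plans to credit the whole difference to resistance exercise. The documents support neither.
3. **Some of the contact is treatment.** The wristband, prompts and technique correction belong to the tested package, so they should not be read simply as confounding. Agreed, and the devices and prompts are not counted above. But a contact that belongs to the treatment is still not balanced by the control, which is what Section 4.3.2 claims.
4. **No bias is sized.** A contact count does not show how far PCS, MCS, FES-I or VAS would move, and the documents give no figure for that. This stands.

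None of these makes the sentence in Section 4.3.2 correct.

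**Conclusion.** The balance claim is wrong as written. Planned in-person contact over 8 months is roughly 35 to 61 in the intervention arm against about 10 in the control arm: a ratio of about 3 to 6, centrally about 5, and about 2 when the matched remote contacts are included. This assumes that the stated frequencies hold for the full 8 months and that the weekly session is in person, as the table says. No reading gives balance.

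The consequence is limited. The whole-programme effect remains estimable without confounding by baseline differences. DXA BMD is little affected, and neither the sample size nor the analysis changes. What is lost is the ability to separate resistance training alone from added staff contact in SF-36 PCS and MCS, FES-I and VAS, given participants who are not described as blinded. No later analysis can recover it, because the two are delivered together. The direction and size of any attention effect are unknown.

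**What to change.** 1. Delete the balance sentence in Section 4.3.2, or confine it to the weekly remote contact and the monthly lecture.
2. Reconcile the contact descriptions in Section 4.3.1 and Table 4.3.1 (1): the weekly offline session against monthly on-site supervision, and whether the group class and the lecture are one event.
3. State that the contrast is the whole programme (training, devices and added contact) against health education, and that differences in SF-36, FES-I and VAS will not be attributed to resistance training alone.
4. Log the number and minutes of staff contact per participant in both arms from the start of the intervention, and report them by arm. The process indicators in Section 4.4.2 and the fidelity checklist in Section 4.3.3 cover training, not control-arm contact. Minutes cannot be reliably reconstructed afterwards.

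The cost is wording, a small logging burden and a narrower quality-of-life claim. The log would also serve the micro-costing in Section 2.4.4, which already needs community worker time. The control arm need not be redesigned.
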